## **8.7. Leicester Cough Questionnaire**

The Leicester Cough Questionnaire (LCQ) is a subject self-report, health related quality of life questionnaire (see [Appendix 14.2](#)) that will be collected per SOA (see [Appendix 14.1](#)). The LCQ consists of three domains where domain scores are equal to the total score from the questions in the domain divided by the number of questions in the domain (domains scores range from 1 to 7):

1. Physical: Questions 1, 2, 3, 9, 10, 11, 14, and 15
2. Psychological: Questions 4, 5, 6, 12, 13, 16, and 17
3. Social: Questions 7, 8, 18, and 19

LCQ total score is equal to the sum of the domain scores (total score range from 3 to 21) with a lower score indicating greater impairment of health status due to cough. The LCQ domain and total scores will be derived for use during analysis. If a response is not provided to a question, the domain score will be calculated as the average of the scores to the answered questions within the domain. If a subject responds to less than 80% of questions in a domain, the LCQ domain score will not be calculated and will be treated as missing during analysis. If it is not possible to calculate all domain scores following this criteria, total score will not be calculated and will be treated as missing during analysis.

Descriptive statistics for observed and change from baseline values will be presented for LCQ domain and total scores by scheduled visit and treatment (active treatments, active treatment total, and pooled placebo) and overall for the Safety Set.

LCQ data will be presented in a listing for the Safety Set.

## **8.8. Cough Visual Analogue Scale**

The cough VAS is a 100 mm scale (See [Appendix 14.3](#)) on which a subject will be asked to mark between 'no cough' (0 mm) and 'the worst cough severity' (100 mm).

Descriptive statistics for observed and change from baseline values will be presented for cough severity VAS by scheduled visit and treatment (active treatments, active treatment total, and pooled placebo) and overall for the Safety Set.

Cough VAS data will be presented in a listing for the Safety Set.

## **9. Pharmacokinetics**

Plasma and BAL samples for PK assessment will be collected as indicated in the SOA (see [Appendix 14.1](#)). Plasma PK analyses and BAL bioanalytical results will be covered by a vendor reported by the sponsor in a separate document.

## **10. Exploratory Biomarker Sampling**

Exploratory biomarkers will be assessed in peripheral blood cells (as feasible), platelet rich plasma, BALF, BA samples, and deep bronchial brushings as outlined in Table 2. Ribonucleic acid (RNA) transcription analysis from whole blood may be substituted for any assays using peripheral blood cells. Samples will be collected at the time of bronchoscopy during the screening period and Day 14 as shown in [Appendix 14.1](#). Additional biomarkers may be added as new information is generated about the potential effects of CSD (caveolin-1 scaffolding domain) signaling.

**Table 2: Exploratory Biomarkers by Sample Source and Assumed Indicator Function**

Sample source / Indicator of	Epithelial damage / repair	Fibrosis	Inflammation	Thrombosis
Peripheral blood cells b	-	p-AKT b , IL-11	CXCL7	-
Platelet rich plasma (PRP)	CYFRA 21-1, SP-D, CA-19-9, KL-6, sRAGE, Galectin 7	MMP-7, Tenascin C (TNC), Periostin, IL-11, MYDGF, MMP-2	CCL18, CXCL13, sICAM1, IL-11, sCD163, CXCL7	PAI-1
BAL and/or BA a	Galectin 7, SP-D, sRAGE	MYDGF, MMP-2, TNC, MMP-7, periostin, IL-11	CCL18, CXCL13, sICAM1, IL-11, sCD163, CXCL7	PAI-1
Deep bronchial brushings	-	p-SMAD2/3	-	-

Abbreviations: BAL = bronchoalveolar lavage. BA = bronchoabsorption

a LTI-03 levels will also be measured on BAL samples. LTI-03 will not be measured in BA samples.

b Ribonucleic acid transcription analysis may be substituted for assays using peripheral blood cells.

For each PD biomarker, concentrations, change from baseline, percent change from baseline, and/or fold change, as applicable, will be summarized by scheduled visit and treatment (active treatments, active treatment total, and pooled placebo) and overall for all subjects in the Safety Set.

Biomarker results that are Below the Limit of Quantification will be treated as zero for calculation of concentration descriptive statistics. Percent change and fold change will be estimated for subjects with both baseline and post-baseline results, but will not be estimated in cases where the baseline result is zero.

Biomarker data will be presented in a listing for the Safety Set.

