### **3.2.3. Exploratory Endpoints**

- To determine the plasma peak and trough concentration of LTI-03 after the first dose and at steady state.

- Change from baseline over time for biomarkers related to the pathophysiology of IPF.

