## 4. General Statistical Considerations

This section presents general rules for the derivation and reporting of study data. If a subsequent section related to a specific derivation or analysis differs from this general guidance, the subsequent section takes precedence.

Continuous data will be presented using descriptive statistics (i.e. n, mean, standard deviation, median, minimum, and maximum). Categorical data will be presented using frequency counts and percentages in each category. For the summary statistics of all numerical variables (unless otherwise specified), minimum and maximum will be displayed to the same level of precision of the raw data. Mean and median will be displayed to one level of precision greater than the data collected. Standard deviation will be displayed to two levels of precision greater than the data collected.

When count data are presented, the percentage will be suppressed when the count is zero in order to draw attention to the non-zero counts. A row denoted “Missing” will be included in count tabulations where specified on the shells to account for missing values. The denominator for all percentages will be the number of subjects in that treatment group within the analysis set of interest, unless otherwise specified. Percentages will be presented to one decimal place except for the display of 100% frequency which will be displayed as ‘XX (100)’.

In general, all tables will be presented by treatment (active treatments, active treatment total, and pooled placebo). Subjects from all cohorts who took placebo will be combined to form a pooled placebo group for analyses. All study data will be presented in by-subject data listings.

“No data available for this report” will be presented when there are no data available to report.

The primary endpoint of the study is safety and no formal statistical hypotheses will be tested.

All descriptive statistical analyses will be performed using Statistical Analysis System (SAS) statistical software (version 9.4 or higher). Missing data will not be imputed unless otherwise stated.

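### The SAP's below-quantification rule counts falls to BLQ as −100% but drops rises from BLQ, so biomarker percent and fold change are biased downward within arm

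*SAP*

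**What the plan says.** The exploratory endpoint in SAP Section 3.2.3 is "Change from baseline over time for biomarkers related to the pathophysiology of IPF". Section 10 schedules one baseline sample, at the screening bronchoscopy, and one on Day 14. For each marker it plans to summarise "concentrations, change from baseline, percent change from baseline, and/or fold change, as applicable", by visit and treatment.

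Three statements after Table 2 of Section 10 decide how BLQ results are handled:

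- "Biomarker results that are Below the Limit of Quantification will be treated as zero for calculation of concentration descriptive statistics".
- The two relative measures, percent and fold change, need a result at each of the two visits.
- These two measures "but will not be estimated in cases where the baseline result is zero".

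The document history shows that the BLQ rule came in with SAP Version 2.0. The comparator follows Section 4: "Subjects from all cohorts who took placebo will be combined to form a pooled placebo group for analyses". Section 4.3 gives 9 subjects on LTI-03 and 3 on placebo per cohort, so 9 per dose against 6 pooled placebo. No formal hypothesis is tested.

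**The concern.** The rule treats the two directions differently. A baseline of zero in practice means a BLQ baseline, so the exclusion removes every subject who started BLQ, including all who rose to a measurable value. A subject who started measurable and became BLQ has a valid denominator and enters at −100%. Removing the low baselines also leaves a group that tends to drift down by regression to the mean.

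Section 10 has nothing to offset this: no positive substitute, log-scale or censored-data method, count of BLQ or excluded subjects, or sensitivity analysis.

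The direction matters because the Protocol (Section 1.1.1.2) describes LTI-03 as lowering profibrotic signals and fibrosis-associated proteins, tenascin-C among them, and tenascin-C is a Table 2 marker. For such markers a fall is the hoped-for result, and falls are what the rule exaggerates.

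The wording also leaves a gap. The zero rule is stated for concentration statistics, and the SAP never says outright what a BLQ Day 14 value becomes in a percent or fold change. The zero-baseline exclusion makes sense only if the zero carries over, which is the natural reading used below.

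**Working it through.** **Inputs from the SAP.** BLQ = 0; percent and fold change not computed when baseline = 0; one baseline and one Day 14 value; 9 active per dose and 6 pooled placebo. Section 10 states no figure of its own to reproduce.

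**Formulas.** With baseline B, Day 14 value D and quantification limit LLOQ: D* = 0 if D < LLOQ, otherwise D; a subject is kept only if B ≥ LLOQ; percent change = 100 × (D*/B − 1); fold change = D*/B.

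**Hand example, no net change.** Nine subjects, LLOQ = 10: two go from BLQ to 20, two from 20 to BLQ, five stay at 20.

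- Mean absolute change = (2×20 − 2×20 + 5×0)/9 = 0.
- Under the SAP rule 7 are kept. Mean percent change = (2×(−100) + 5×0)/7 = −28.6%; mean fold change = 5/7 = 0.71.
- With LLOQ/2 = 5 at both visits the log ratios are +ln 4 twice, −ln 4 twice and 0 five times, so the geometric mean ratio is 1.00.
- The arithmetic mean percent change with the same substitute is (2×300 − 2×75)/9 = +50%. Substitution therefore needs the log scale as well.

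**Simulation.** Assumed, because the documents give none of these: log-normal pairs, CV 60% (log-SD = √ln(1 + 0.6²) = 0.55), correlation 0.7, LLOQ at the 10th/30th/50th percentile of baseline. The within-arm column uses 1,000,000 pairs per scenario. The contrast column uses 200,000 simulated trials of 9 versus 6 and is the mean difference in median fold change, in points.

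| True change | SAP median, within arm | Active minus placebo |
|---|---|---|
| None | −3% / −8% / −14% | −0.6 / +0.7 / +0.4 |
| −25% | −29% / −38% / −60% | −28 / −37 / −42 |
| −50% | −66% / −100% / −100% | −70 / −82 / −74 |
| +50% | +45% / +38% / +31% | +49 / +51 / +56 |

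Repeat runs put the −60% entry between −60% and −62%; the other entries are stable.

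- With no effect, the arithmetic mean percent change is +2%/−9%/−20%, against +10% uncensored. Mean absolute change stays about 0.
- At the 30th percentile, 6.3 of 9 active and 4.2 of 6 placebo subjects are kept on average; 3 or fewer placebo subjects are left in 26% of trials.

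**Dependence on the assumptions.** The no-effect median at the 30th percentile is −13.4% at correlation 0.5, −2.8% at 0.9, and −11.9% at CV 100% with correlation 0.7. A wider grid had 72 settings: log-SD 0.5–1.0, correlation 0.3–0.8, baseline BLQ share 10–50%, true fold change 0.7, 1.0 or 1.5. In every one, both the SAP mean and the SAP median lay below their uncensored values. With no true change the median ran from −1.9% to −54.7%, and the mean was 5 to 117 points too low.

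**The case against.** **The size is assumed.** This stands. No LLOQ, BLQ rate, variance or correlation is given. The largest figures also need heavy censoring: in the halving scenario 49%/77%/89% of Day 14 values are BLQ, so a −100% median partly says that the assay cannot measure the marker. The direction does not depend on this; the size does.

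**The samples are too small for it to show.** Partly stands. With no effect, the 8-point shift at the 30th percentile compares with an SD of 24 points for one 9-subject median. For a true 25% fall the uncensored small-sample contrast is −26.5 points, so the excess is about 1.5/10/15 points against contrast SDs of 28/43/54. For a halving the uncensored contrast is −52 and the excess about 19/30/23 points against SDs of 31/35/43. Noise does not justify a one-sided rule, and a shift in the same direction can recur across the many markers in Table 2.

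**Other outputs reveal it.** Concentrations, absolute change and the listing keep the BLQ-baseline subjects, and a reduced n or a minimum of −100% would alert a careful reader. The endpoint is worded as change, and percent and fold change are planned only as applicable. All true, but none of it corrects the percent and fold-change tables. Absolute change is not immune either: for a true halving, zero substitution gives −0.71/−0.75/−0.69 against about −0.58 uncensored (baseline median = 1).

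**Placebo cancels it.** True on average under no effect, and little is lost against placebo for a true rise. It fails for a true fall.

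**Conclusion.** The concern holds. On the natural reading of SAP Section 10, within-arm percent and fold change are biased downward relative to the same summaries on uncensored data whenever some results are BLQ. Under the assumed model, with the limit at the 10th to 50th percentile of baseline, the null median shifts by 3 to 14 points, a true halving appears as a 66% to 100% fall, and a true 50% rise is understated at +45% to +31%. Against pooled placebo the null bias roughly vanishes, but a true halving is overstated by about 20 to 30 points.

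Downward does not mean below zero in every case: at the 10th percentile the null arithmetic mean is still +2%, because ratios are right-skewed. The biomarkers are exploratory and nothing is tested, so what suffers is the reading of the pharmacodynamic results. It should be fixed because the fix is cheap.

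**What to change.** In SAP Section 10:

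1. Keep the zero rule for concentration summaries only, and say so.
2. For change measures, replace BLQ by the same positive value, for example LLOQ/2, at both baseline and Day 14, and keep subjects with a BLQ baseline.
3. Summarise change as the log ratio, reported as the geometric mean ratio to baseline, by dose and for pooled placebo.
4. Report the number BLQ at each visit per arm beside each estimate.
5. Add one sensitivity run with LLOQ as the substitute.

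**Cost.** A few sentences, one reprogrammed table and the sensitivity run repeated across markers. A footnote should explain that mean change will no longer equal the difference between mean concentrations.

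**Downside.** The substitute is arbitrary. Any common positive value gives a ratio of 1.00 under no effect by symmetry, so that is no evidence for LLOQ/2 in particular. Under a true effect both choices are approximate (limit at the 10th/30th/50th percentile):

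| True ratio | LLOQ/2 | LLOQ |
|---|---|---|
| 0.50 | 0.46 / 0.53 / 0.63 | 0.60 / 0.73 / 0.82 |
| 0.75 | 0.72 / 0.73 / 0.78 | 0.78 / 0.84 / 0.89 |
| 1.50 | 1.55 / 1.59 / 1.56 | 1.47 / 1.39 / 1.30 |

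That is why the BLQ counts must stand beside the estimates: where many values are BLQ, no substitute yields a reliable size of change.

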## 11. Interim Analysis

No formal interim analyses are planned for the study. Cohort 1 biomarker data may be analyzed before final database lock without changing the overall study conduct. If required, these analyses will be handled by Lung Therapeutics. PPD Biostatistics will provide relevant blinded SDTM and ADaM datasets to Lung Therapeutics to conduct the analyses. If requested, unblinded PPD Biostatistics personnel will be assigned and appropriate documentation updated to detail the unblinding event.

## **12. Changes in the Planned Analysis**

Section 8.6: Line graphs of 15% Baseline FEV1 is updated to 15% decrease from Baseline FEV1.

## 14. Appendices

### 14.1. Schedule of Assessments

	Screening Period	Treatment Period 			Follow-Up	Early Termination 
		(Day -21 to Day -1)	Day 1	Day 7 ( $\pm 1$ day)	Day 14 ( $\pm 1$ day)	
Informed consent	x					
Inclusion/Exclusion Criteria	x	x				
Demographics, Medical History	x					
Prior medications	x					
Concomitant medications						
Complete physical examination 	x			x		x
Brief physical examination 		x	x		x	
Vital Signs	x	x	x	x	x	x
ECG (12-Lead ECG), single	x	x	x	x	x	x
Bronchoscopy with BAL and/or BA and deep bronchial brushings biopsy	x			x		x
Blood for biomarker assessments 	x			x		x
Pregnancy test 	x	x	x	x	x	x
Safety Laboratory parameters 	x	x	x	x	x	x
Randomization		x				
Blood collection for PK 		x	x	x		
Assessment of ability to use inhaler	x					
Leicester Cough Questionnaire & Cough VAS	x	x	x	x	x	x
Spirometry 	x	x	x	x	x	x

Dosing 		x	x	x		
Subjects returning unused study drug			x	x		
Adverse Events	x			x		

Abbreviations: BAL = bronchoalveolar lavage; BA = bronchoabsorption; DLCO = diffusion capacity of the lungs for carbon monoxide; ECG = electrocardiogram; PK = pharmacokinetics; VAS = visual analogue scale

**Note:**

1. On Days 2 to 6 and Days 8 to 13, subjects will self-administer study drug at home and will be contacted on Day 4 ( $\pm$  2 days) and Day 10 ( $\pm$  2 days) by study staff to check on compliance and for potential adverse events. Day 1, 7, and 14 will be clinic visit. Study be clinic visit. Study staff will monitor subjects self-administrating study drug (most likely the morning dose) on Day 1, Day 7, and Day 14.
2. If a subject discontinues study drug before Day 14, the Day 14 assessments (other than study drug dosing) where feasible should be performed in the clinic as close as possible to the day of discontinuation. The EOS assessments should be performed 7 days after the last dose of study drug (assuming the subject has not withdrawn consent).
3. A complete physical examination will include an evaluation of the head, eyes, ears, nose and throat, and the cardiovascular, dermatologic, musculoskeletal, respiratory, gastrointestinal, and neurologic systems. Any abnormality identified at baseline (Screening Day) will be recorded as medical history.
4. A brief physical examination will focus on systems affected by AEs and at a minimum should include the cardiovascular and respiratory systems.
5. Biomarker assessment will be for peripheral blood cells, platelet rich plasma, bronchoalveolar lavage fluid (BALF), BA samples, and deep bronchial brushings.
6. Serum or urine test required for any FOCBP, defined as pre-menopausal or  $<$  12 months of amenorrhea post-menopause or no history of surgical sterilization.
7. Safety laboratory assessments include hematology, chemistry, and coagulation. Coagulation will be performed only at Screening.
8. Blood for PK will be collected pre-dose (trough) and +5 minutes after dosing (peak).
9. Spirometry: DLCO on Screening only. On treatment days (Day 1, 7, 14), it will be done before dosing and post dose at 30 and 60 minutes.
10. Study staff will monitor subjects self-administrating study drug (most likely the morning dose) on Day 1, Day 7, and Day 14. On Day 1, the first dose of study drug will be administered at the investigational site and subjects will be monitored for at least 1 hour after dosing. Study drug is dispensed on Day 1 and Day 7.

## 14.2. Leicester Cough Questionnaire

This questionnaire is designed to assess the impact of cough on various aspects of your life. Read each question carefully and answer by CIRCLING the response that best applies to you. Please answer ALL questions, as honestly as you can.

1. In the last 2 weeks, have you had chest or stomach pains as a result of your cough?

1 All of the time	2 Most of the time	3 A good bit of the time	4 Some of the time	5 A little of the time	6 Hardly any of the time	7 None of the time
----------------------	-----------------------	-----------------------------	-----------------------	---------------------------	-----------------------------	-----------------------

2. In the last 2 weeks, have you been bothered by sputum (phlegm) production when you cough?

1 Every time	2 Most times	3 Several times	4 Some times	5 Occasionally	6 Rarely	7 Never
-----------------	-----------------	--------------------	-----------------	-------------------	-------------	------------

3. In the last 2 weeks, have you been tired because of your cough?

1 All of the time	2 Most of the time	3 A good bit of the time	4 Some of the time	5 A little of the time	6 Hardly any of the time	7 None of the time
----------------------	-----------------------	-----------------------------	-----------------------	---------------------------	-----------------------------	-----------------------

4. In the last 2 weeks, have you felt in control of your cough?

1 None of the time	2 Hardly any of the time	3 A little of the time	4 Some of the time	5 A good bit of the time	6 Most of the time	7 All of the time
-----------------------	-----------------------------	---------------------------	-----------------------	-----------------------------	-----------------------	----------------------

5. How often during the last 2 weeks have you felt embarrassed by your coughing?

1 All of the time	2 Most of the time	3 A good bit of the time	4 Some of the time	5 A little of the time	6 Hardly any of the time	7 None of the time
----------------------	-----------------------	-----------------------------	-----------------------	---------------------------	-----------------------------	-----------------------

6. In the last 2 weeks, my cough has made me feel anxious

1 All of the time	2 Most of the time	3 A good bit of the time	4 Some of the time	5 A little of the time	6 Hardly any of the time	7 None of the time
----------------------	-----------------------	-----------------------------	-----------------------	---------------------------	-----------------------------	-----------------------

7. In the last 2 weeks, my cough has interfered with my job, or other daily tasks

1 All of the time	2 Most of the time	3 A good bit of the time	4 Some of the time	5 A little of the time	6 Hardly any of the time	7 None of the time
----------------------	-----------------------	-----------------------------	-----------------------	---------------------------	-----------------------------	-----------------------

8. In the last 2 weeks, I felt that my cough interfered with the overall enjoyment of my life

1 All of the time	2 Most of the time	3 A good bit of the time	4 Some of the time	5 A little of the time	6 Hardly any of the time	7 None of the time
----------------------	-----------------------	-----------------------------	-----------------------	---------------------------	-----------------------------	-----------------------

9. In the last 2 weeks, exposure to paints or fumes has made me cough

1 All of the time	2 Most of the time	3 A good bit of the time	4 Some of the time	5 A little of the time	6 Hardly any of the time	7 None of the time
----------------------	-----------------------	-----------------------------	-----------------------	---------------------------	-----------------------------	-----------------------

10. In the last 2 weeks, has your cough disturbed your sleep?

1 All of the time	2 Most of the time	3 A good bit of the time	4 Some of the time	5 A little of the time	6 Hardly any of the time	7 None of the time
----------------------	-----------------------	-----------------------------	-----------------------	---------------------------	-----------------------------	-----------------------

11. In the last 2 weeks, how many times a day have you had coughing bouts?

1 All of the time (continuously)	2 Most times during the day	3 Several times during the day	4 Some times during the day	5 Occasionally through the day	6 Rarely	7 None
--	-----------------------------------	--------------------------------------	-----------------------------------	--------------------------------------	-------------	-----------

12. In the last 2 weeks, my cough has made me feel frustrated

1 All of the time	2 Most of the time	3 A good bit of the time	4 Some of the time	5 A little of the time	6 Hardly any of the time	7 None of the time
----------------------	-----------------------	-----------------------------	-----------------------	---------------------------	-----------------------------	-----------------------

13. In the last 2 weeks, my cough has made me feel fed up

1 All of the time	2 Most of the time	3 A good bit of the time	4 Some of the time	5 A little of the time	6 Hardly any of the time	7 None of the time
----------------------	-----------------------	-----------------------------	-----------------------	---------------------------	-----------------------------	-----------------------

14. In the last 2 weeks, have you suffered from a hoarse voice as a result of your cough?

1 All of the time	2 Most of the time	3 A good bit of the time	4 Some of the time	5 A little of the time	6 Hardly any of the time	7 None of the time
----------------------	-----------------------	-----------------------------	-----------------------	---------------------------	-----------------------------	-----------------------

15. In the last 2 weeks, have you had a lot of energy?

1 None of the time	2 Hardly any of the time	3 A little of the time	4 Some of the time	5 A good bit of the time	6 Most of the time	7 All of the time
-----------------------	-----------------------------	---------------------------	-----------------------	-----------------------------	-----------------------	----------------------

16. In the last 2 weeks, have you worried that your cough may indicate serious illness?

1 All of the time	2 Most of the time	3 A good bit of the time	4 Some of the time	5 A little of the time	6 Hardly any of the time	7 None of the time
----------------------	-----------------------	-----------------------------	-----------------------	---------------------------	-----------------------------	-----------------------

17. In the last 2 weeks, have you been concerned that other people think something is wrong with you, because of your cough?

1 All of the time	2 Most of the time	3 A good bit of the time	4 Some of the time	5 A little of the time	6 Hardly any of the time	7 None of the time
----------------------	-----------------------	-----------------------------	-----------------------	---------------------------	-----------------------------	-----------------------

18. In the last 2 weeks, my cough has interrupted conversation or telephone calls

1 Every time	2 Most times	3 A good bit of the time	4 Some of the time	5 A little of the time	6 Hardly any of the time	7 None of the time
-----------------	-----------------	-----------------------------	-----------------------	---------------------------	-----------------------------	-----------------------

[figure not shown]
19. In the last 2 weeks, I feel that my cough has annoyed my partner, family or friends

1 Every time I cough	2 Most times when I cough	3 Several times when I cough	4 Some times when I cough	5 Occasionally when I cough	6 Rarely	7 Never
-------------------------	------------------------------	---------------------------------	------------------------------	--------------------------------	-------------	------------

Thank you for completing this questionnaire.

